## **Part I: Type of research study**

- New research study  
 Ongoing research project

### **3. Type of research**

Clinical trial

### **4. Academic disciplines and research subjects**

Medical Sciences (Dermatology)

### **5. Keywords**

Alopecia areata, Alopecia totalis, Alopecia universalis, Tofacitinib, JAK inhibitor

### **6. The importance of the research problem and its origin**

Alopecia areata (AA) is a condition that causes sudden hair loss, primarily affecting the scalp and beard but can be on any part of the body. This condition affects 0.2% of the population and can occur in all age groups and both genders. From outpatient statistical data at the Institute of Dermatology, a total of 2,406 patients with patchy AA were treated in 2012, 3,079 patients in 2013, 2,814 patients in 2014, and 1,887 patients in 2015. Three hundred forty-nine extensive AA cases were treated in 2012, 654 in 2013, 691 in 2014, and 455 in 2015. The cause of the disease remains unknown. It is believed to be an autoimmune disorder caused by an abnormal immune response to hair follicle correlated antigens. Interferon-gamma (IFN- $\gamma$ ) is an important cytokine inducing and tampering normal immune privilege of the anagen hair bulb to collapse, therefore triggering the hair follicle destruction.

AA presents in the shape of oval or round, well-circumscribed, bald patches anywhere all over the scalp. Hair loss can extend to the entire scalp, called alopecia totalis, and alopecia universalis is the loss of all scalp hair and body hair. It can cause embarrassment and affects the quality of life.

There are a few efficacy data for robust treatment of AA. An expert consensus seems to treat localized AA with intralesional and topical corticosteroids. In extensive AA, alopecia totalis, and alopecia universalis, diphenycyclopropenone or Janus kinase (JAK) inhibitors are good treatment options. Other options include the combination of short contact anthralin and topical minoxidil or high potency topical corticosteroids with topical minoxidil. Clinical improvement after applying short contact anthralin and topical minoxidil is approximately 75% in the case of patchy AA and 25% in the case of extensive AA, similar to that of topical corticosteroids with minoxidil. There is a 25% chance of hair growth. Systemic corticosteroids may be used to treat severe AA with methotrexate, cyclosporine, or azathioprine but should not be used as a routine long-term treatment because of the risk of side effects. However, those treatments may not be effective for recalcitrant cases. Recently, Janus kinase (JAK) inhibitors such as tofacitinib and ruxolitinib have been used to treat patients with extensive AA. Many studies found that patients with AA had more significant hair growth (>50%) by 54-81.9% after taking tofacitinib. JAK inhibitors are expected to reduce interferon- $\gamma$  and interleukin-15, causing fewer white blood cells to destroy hair follicles.

The effectiveness of tofacitinib for AA treatment has not been studied in Thailand, and only a few studies reported it in Asians. Although tofacitinib may be a choice in AA standard guidelines, the price of this medication may not be affordable. It is essential to prove the effectiveness to generate concrete evidence for the debates and stakeholders' consideration in the cost-effectiveness of tofacitinib for extensive AA.

## **7. The objective of this study**

### **7.1 Primary objective**

To study the effectiveness and safety of tofacitinib in Thai patients with recalcitrant and extensive AA at 24 weeks

### **7.2 Secondary objectives**

To measure the quality of life in economic evaluation in Thai patients with recalcitrant and extensive AA treated with tofacitinib

## **8. The scope of this study**

### **8.1 Study population**

8.1.1 Specific disease or condition(s): Subjects with extensive and recalcitrant AA coming to the hair and nail clinic and outpatient department at the Institute of Dermatology

8.1.2 Gender: Male and Female

8.1.3 Age: Subjects aged 18 years or older

8.1.4 Number of subjects: calculated from the formula

$$n = \frac{Z_{\alpha/2}^2 P(1-P)}{d^2}$$

$$Z_{\alpha/2} = 1.96$$

$$P = \text{Proportion of the population who had improvement} = 0.87$$

$$d = \text{A maximum tolerated error determined by an investigator} = 0.2$$

$$n = \frac{(1.96)^2(0.8)(1-0.8)}{(0.2)^2} = 16$$

Therefore, the number of subjects should be approximately 16. Given approximately 20% of the number of patients who may have missed follow-up treatments, a total of 19 subjects are planned to be collected.

## **8.2 Selection criteria**

### 8.2.1 Inclusion criteria

8.2.1.1 Thai subjects aged 18 years or over

8.2.1.2 Subjects with extensive AA greater than 50% of the scalp

8.2.1.3 Subjects who can come for follow-ups during the first 6 months of treatment

8.2.1.4 Subjects who are unresponsive to diphenylcyclopropenone, anthralin, clobetasol cream, and topical minoxidil for at least 6 months.

### 8.2.2 Exclusion criteria

8.2.2.1 Subjects with hair loss from other causes, e.g., Telogen effluvium, Trichotillomania, onychomycosis (Tinea capitis)

8.2.2.2 Subjects with chronic or severe disease with unstable symptoms that may affect hair condition during the 6 months prior to screening, such as thyroid diseases, iron deficiency anemia, liver diseases (subjects with chronic hepatitis but with stable symptoms can participate in the study), heart diseases, neurological diseases, digestive disorders, reproductive diseases, cancer, and psychiatric diseases

8.2.2.3 Subjects who had been treated for AA with topical corticosteroids or topical anthralin or diphenylcyclopropenone within 1 month prior to screening, or subjects who had been treated for AA with systemic corticosteroids or any other oral medication during 3 months before screening

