8.3.2 Research period: January 2019 - January 2021

## **9. Theories, hypotheses and conceptual frameworks of this study**

Alopecia areata (AA) is a condition in which the body's immune system is sensitive to itself. The in vitro studies showed this natural killer gene 2D-expression CD8+ T cell is the leading cause of an increase in interleukin-15 in the hair follicle, increasing interferon- $\gamma$  and leading to hair follicle destruction.

The standard guideline for extensive AA includes diphenylcyclopropenone, short contact anthralin, high potency topical corticosteroids. A recent study found that the combination therapy between diphenylcyclopropenone and anthralin was more effective than diphenylcyclopropenone monotherapy (55% vs. 88). However, the chance of treatment response is approximately 25-50%, upon the severity and duration of the disease. The diphenylcyclopropenone powder is expensive and must be mixed with acetone or alcohol solution before use in different concentrations. The high cost of diphenylcyclopropenone and the difficulty of mixing in different concentrations are why diphenylcyclopropenone solutions are unavailable in most hospitals. Most of the patients, especially those in the provincial areas, could not access such services. Inaccessible diphenylcyclopropenone treatment leads to inappropriate use of systemic corticosteroids. The successful rate of using systemic corticosteroids is only 43%, with a 17% chance of relapse. Nevertheless, many patients have poor clinical improvement after receiving various therapies. Those patients have reduced their quality of life, lost their self-confidence, and could develop stress, anxiety, and depression.

Tofacitinib is a potent, selective inhibitor of the Janus Kinase (JAK) family of kinases and was approved by US Food and Drug Administration to treat adults with moderate to severe rheumatoid arthritis. This medication can inhibit signaling by receptors associated with JAK3 and/or JAK1. The inhibition of JAK3 and/or JAK1 disrupts the signals of interferon- $\gamma$  and interleukin-15 between white blood cells (WBC) and the nucleus of hair follicle cells, slowing down the production of WBC type CD8+NKG2D+ T cell, one of the causes of hair loss.

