### 13.2 Conducting research procedures

13.2.1 The principal investigator selects the volunteers according to the inclusion and exclusion criteria.

13.2.2 The principal investigator takes a personal history of the volunteers, such as date of birth, age, ethnicity, age of onset, stage of disease progression, past medical history, weight, and height.

13.2.3 The principal investigator will ask the volunteers about their health, pre-existing disease conditions such as allergies, asthma, thyroid disease, psoriasis, vitiligo, autoimmune diseases, rheumatoid arthritis, diabetes, irritable bowel syndrome, immunodeficiency states, current medications, or medications taken or treated prior to the administration for 1 month, severe illness and severe stress.

13.2.4 The principal investigator examines the condition of the scalp, hair, and body by measuring the area of hair loss on the scalp, including the body hair by recording the SALT score, hair loss on the body, and examining the nail characteristics.

$$\frac{\text{SALT BL} - \text{SALT F/U}}{\text{SALT BL}} \times 100\% = \% \text{ change from baseline.}$$

13.2.5 All subjects will have photos taken from the side, back, and top of their scalp with a stereotactic device.

13.2.6 All subjects will undergo tests prior to treatment, including complete blood count, lipid profiles, anti-HIV, HBs Ag, Anti HCV, renal function test (BUN, Cr), liver function test (LFT), urine pregnancy test (UPT; female), chest x-ray, stool exam.

13.2.7 All subjects will be asked to take Tofacitinib 5 mg twice a day.

13.2.8 All subjects will be evaluated after the treatment every four weeks during the 24-week duration of the treatments. The SALT score is assessed each time, including the potential side effects. Also, they will have photos taken from the side, back, and top of their scalp with a stereotactic device every visit. The treatment with tofacitinib is successful should subjects have hair regrowth more than 50% compared to the baseline photo.

13.2.9 All subjects are required to have blood tests later for CBC, cholesterol, triglyceride, low-density lipoprotein (LDL), LFT, BUN, and Cr after weeks 4, 12, 24 of treatments.

13.2.10 All female subjects are required to have UPT every four weeks during the 24-week duration of the treatments.

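### The prior-drug exclusion in 8.2.2.3 depends on why the drug was given, so recent systemic immunosuppression for another stable disease is not excluded on this ground

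*Combined protocol and SAP*

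**What the plan says.** Section 8.2.2.3 has two parts, and both depend on indication. The topical part covers subjects "treated for AA with topical corticosteroids or topical anthralin or diphenylcyclopropenone within 1 month prior to screening". The systemic part covers "subjects who had been treated for AA with systemic corticosteroids or any other oral medication during 3 months before screening". The catch-all for other oral drugs falls under the same condition.

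The neighbouring criterion, 8.2.2.2, concerns disease and not drugs: "Subjects with chronic or severe disease with unstable symptoms that may affect hair condition during the 6 months prior to screening". Inclusion criterion 8.2.1.4 concerns only failure of listed topical treatments. I found no rule on systemic drugs given for other diseases, before entry or during the 24 weeks.

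Section 6 states: "Systemic corticosteroids may be used to treat severe AA with methotrexate, cyclosporine, or azathioprine". Section 9 adds a figure: "The successful rate of using systemic corticosteroids is only 43%, with a 17% chance of relapse".

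At entry, 13.2.3 asks about "pre-existing disease conditions such as allergies, asthma, thyroid disease, psoriasis, vitiligo, autoimmune diseases, rheumatoid arthritis" and about "current medications, or medications taken or treated prior to the administration for 1 month". No eligibility or analysis consequence is attached to the answers. Under 13.2.7 every subject takes tofacitinib. Under 13.2.8 success is more than half regrowth against the baseline photograph, with no condition on other drugs.

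**The concern.** A drug acts on the follicle whatever the reason for prescribing it. The 3-month window shows that the authors regard recent systemic treatment as a source of confusion, yet the rule is switched on by the label on the prescription. The protocol's own background names the drugs that the rule can miss.

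Two results are at stake. The first is the response rate: no comparator arm shares the background effect, so regrowth caused by another immunosuppressant would be counted as tofacitinib response. The second is safety, which is part of the primary objective in 7.1. Section 9 lists respiratory infection and raised liver enzymes among tofacitinib's side effects. If these arose under combined immunosuppression, they would be reported as effects of tofacitinib alone. Section 13.6 contains no adjustment or sensitivity analysis for either.

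The worry is mainly a drug recently started or increased, before entry or during follow-up.

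**Working it through.** **Step 1: can another criterion catch these subjects?**
- 8.2.2.3 does not, because the drug was not given for AA.
- 8.2.2.2 does so only if the other disease was unstable in the previous 6 months and may affect hair. A subject whose other disease is stable is not caught.
- 8.2.1.4 does not, because it concerns topical treatments.
- 13.2.3 records current drugs and those of the previous month. That is shorter than the 3 months in 8.2.2.3. An oral steroid course for another disease two months before entry is neither excluded nor required by the medication item.

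**Step 2: the plan's own sample size, used here only for scale.** Section 8.1.4 uses n = z²P(1−P)/d². With the substituted P = 0.8 and d = 0.2, this is 1.96² × 0.8 × 0.2 / 0.04 = 15.37, rounded up to 16, which reproduces. Adding 20% gives 16 × 1.2 = 19.2, stated as 19. (The same section lists P = 0.87, which would give 10.86, or 11. That is a separate matter.) A 20% loss from 19 leaves 19 × 0.8 = 15.2, about 15.

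**Step 3: ceiling per subject.** One responder wholly due to another drug moves the rate by 1/19 = 5.3 points, 1/16 = 6.25 points or 1/15 = 6.7 points.

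**Step 4: expected inflation.** Response is yes or no. The other drug therefore adds a responder only when the subject would not have responded to tofacitinib. With k exposed subjects, response r to the other drug, tofacitinib response p and independence:

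inflation = k × r × (1 − p) / n

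Inputs: r = 0.43 (section 9); p = 0.54 to 0.819 (sections 6 and 9); k = 2 is my assumption, since the documents give no number.

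| p | added responders, k = 2 | n = 19 | n = 15 |
|---|---|---|---|
| 0.54 | 2 × 0.43 × 0.46 = 0.40 | 2.1 points | 2.6 points |
| 0.819 | 2 × 0.43 × 0.181 = 0.16 | 0.8 points | 1.0 points |

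For k from 1 to 3 with n = 19, the range is 0.4 points (k = 1, p = 0.819) to 3.1 points (k = 3, p = 0.54). The tolerated error in 8.1.4 is 20 points.

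**The case against.** The strongest case against is that this is a loophole of unknown frequency and small expected effect. Four parts of it stand.

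- **Size.** A reader might multiply two subjects by 43%, get 0.86 extra responders, and conclude that the rate rises by 0.86/19 = 4.5 to 0.86/15 = 5.7 points. That counts subjects who would have responded to tofacitinib anyway, so the documents' own response figures do not support it. The 43% may also be too high here: section 6 says that these treatments may not work in recalcitrant cases, which is the population in 7.1, and section 9 does not tie the figure to such cases.
- **Eligibility.** A reader might infer that someone with a recent steroid course for asthma, or newly started methotrexate for rheumatoid arthritis, meets every criterion. That is not shown. Recent treatment may signal unstable disease, and the list in 8.2.2.2 is open-ended, although its condition about affecting hair leaves room for judgement. The subject on a long-standing stable drug is more clearly admissible, but still has more than 50% scalp loss on that drug, so regrowth from it is less likely.
- **Direction.** A course finished before baseline may be wearing off, and section 9 mentions relapse after systemic corticosteroids. That would lower the apparent response.
- **Recording.** 13.2.3 is a history checklist and does not say that such subjects are expected. It already captures current drugs, so much ongoing exposure would be visible.

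None of this closes the gap. The look-back is shorter than the exclusion window, what is recorded has no stated use, and drugs started or changed during the 24 weeks are not addressed.

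**Conclusion.** The concern holds in a limited form. As worded, 8.2.2.3 does not exclude recent systemic corticosteroids, methotrexate, cyclosporine or azathioprine given for another, stable disease. In a single group their effects cannot be separated from those of tofacitinib.

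The figures in step 4 are illustrations and not estimates of bias in this trial. They rest on an assumed number exposed, on independence of the two responses, and on a 43% figure that may not apply to recalcitrant disease. If nobody is exposed, the effect is nil. On these assumptions the expected inflation is small beside the 20-point tolerated error. The documents do not support reading this as a threat that by itself overturns the response rate. It is worth acting on because one misattributed responder is visible in a group of 19 and the remedy is cheap.

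**What to change.** Reconcile 8.2.2.3 with section 6 and 13.2.3, as follows.

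1. Define the 3-month systemic exclusion by drug: systemic corticosteroids and the systemic immunosuppressants named in section 6, for any indication. Simply striking the reference to AA would not do, because the catch-all would then exclude every oral medication.
2. Extend the medication look-back in 13.2.3 from 1 to 3 months so that it matches the exclusion window.
3. At the four-weekly visits, record any of these drugs started or changed during the 24 weeks.
4. In 13.6, flag exposed subjects and show week-24 response and adverse events with and without them.

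The cost is a short eligibility amendment, a longer history item, one extra item per visit and one sensitivity line. The downside is that a few patients with co-existing inflammatory disease become ineligible. If enrolment is already complete, the flag and the with-and-without comparison are still useful.

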8.2.2.4 Subjects who are pregnant

## **8.3 Research site and study period**

8.3.1 Study site: Hair and Nail Clinic, Institute of Dermatology Department of Medicine Ministry of Public Health, Bangkok

8.3.2 Research period: January 2019 - January 2021

## **9. Theories, hypotheses and conceptual frameworks of this study**

Alopecia areata (AA) is a condition in which the body's immune system is sensitive to itself. The in vitro studies showed this natural killer gene 2D-expression CD8+ T cell is the leading cause of an increase in interleukin-15 in the hair follicle, increasing interferon- $\gamma$  and leading to hair follicle destruction.

The standard guideline for extensive AA includes diphenylcyclopropenone, short contact anthralin, high potency topical corticosteroids. A recent study found that the combination therapy between diphenylcyclopropenone and anthralin was more effective than diphenylcyclopropenone monotherapy (55% vs. 88). However, the chance of treatment response is approximately 25-50%, upon the severity and duration of the disease. The diphenylcyclopropenone powder is expensive and must be mixed with acetone or alcohol solution before use in different concentrations. The high cost of diphenylcyclopropenone and the difficulty of mixing in different concentrations are why diphenylcyclopropenone solutions are unavailable in most hospitals. Most of the patients, especially those in the provincial areas, could not access such services. Inaccessible diphenylcyclopropenone treatment leads to inappropriate use of systemic corticosteroids. The successful rate of using systemic corticosteroids is only 43%, with a 17% chance of relapse. Nevertheless, many patients have poor clinical improvement after receiving various therapies. Those patients have reduced their quality of life, lost their self-confidence, and could develop stress, anxiety, and depression.

Tofacitinib is a potent, selective inhibitor of the Janus Kinase (JAK) family of kinases and was approved by US Food and Drug Administration to treat adults with moderate to severe rheumatoid arthritis. This medication can inhibit signaling by receptors associated with JAK3 and/or JAK1. The inhibition of JAK3 and/or JAK1 disrupts the signals of interferon- $\gamma$  and interleukin-15 between white blood cells (WBC) and the nucleus of hair follicle cells, slowing down the production of WBC type CD8+NKG2D+ T cell, one of the causes of hair loss.

The safety and effectiveness of tofacitinib for AA treatment have been demonstrated in adults. In the three studies, subjects with extensive AA had clinical improvement of about 54-81.9% during the six months, and the Severity of Alopecia Tool (SALT) score was improved by 50-90% approximately.

The side effects of the treatment were mild. Subjects may develop headaches, hyperlipidemia, upper respiratory tract infection, and a slight increase in hepatic enzyme activity. Those side effects usually return to normal even after the patient did not stop taking the drug, and in very few cases, erythema, leg swelling, paleness, bone ischemia have been reported. However, no cancer was found in patients taking the drug yet, though, the company has a warning about this in the drug leaflet.

## 11. Beneficial impact

The researchers anticipate that the research project results will bring new knowledge as a basis for better treatment of hair and scalp conditions and diseases. Clinical outcome data can be used as information for patients to make informed decisions about AA treatments. It is also used in healthcare policy to make decisions and find the most suitable service for patients with recalcitrant AA.

## 12. Plans for transferring technology or results to target groups

12.1. To be published in international medical journals to provide information to the public

12.2. To be presented at academic conferences both in Thailand and abroad

## 13. Methods of conducting research and place for conducting study/data storage

### 13.1 Study design

This is a prospective cohort study conducted at the Institute of Dermatology. Nineteen male and female Thai volunteers with extensive hair loss of more than 50% of the head area were recruited.

### 13.2 Conducting research procedures

13.2.1 The principal investigator selects the volunteers according to the inclusion and exclusion criteria.

13.2.2 The principal investigator takes a personal history of the volunteers, such as date of birth, age, ethnicity, age of onset, stage of disease progression, past medical history, weight, and height.

13.2.3 The principal investigator will ask the volunteers about their health, pre-existing disease conditions such as allergies, asthma, thyroid disease, psoriasis, vitiligo, autoimmune diseases, rheumatoid arthritis, diabetes, irritable bowel syndrome, immunodeficiency states, current medications, or medications taken or treated prior to the administration for 1 month, severe illness and severe stress.

13.2.4 The principal investigator examines the condition of the scalp, hair, and body by measuring the area of hair loss on the scalp, including the body hair by recording the SALT score, hair loss on the body, and examining the nail characteristics.

$$\frac{\text{SALT BL} - \text{SALT F/U}}{\text{SALT BL}} \times 100\% = \% \text{ change from baseline.}$$

13.2.5 All subjects will have photos taken from the side, back, and top of their scalp with a stereotactic device.

13.2.6 All subjects will undergo tests prior to treatment, including complete blood count, lipid profiles, anti-HIV, HBs Ag, Anti HCV, renal function test (BUN, Cr), liver function test (LFT), urine pregnancy test (UPT; female), chest x-ray, stool exam.

13.2.7 All subjects will be asked to take Tofacitinib 5 mg twice a day.

13.2.8 All subjects will be evaluated after the treatment every four weeks during the 24-week duration of the treatments. The SALT score is assessed each time, including the potential side effects. Also, they will have photos taken from the side, back, and top of their scalp with a stereotactic device every visit. The treatment with tofacitinib is successful should subjects have hair regrowth more than 50% compared to the baseline photo.

13.2.9 All subjects are required to have blood tests later for CBC, cholesterol, triglyceride, low-density lipoprotein (LDL), LFT, BUN, and Cr after weeks 4, 12, 24 of treatments.

13.2.10 All female subjects are required to have UPT every four weeks during the 24-week duration of the treatments.

13.2.11 When AA subjects finish treatments either at week 24, or resolved before, or discontinue tofacitinib due to the side effects before the end of the treatments, they are required to have a follow-up after four weeks of discontinuation.

